### **8. SAMPLE SIZE**

This study will identify patients diagnosed with an intestinal emergency who may require surgery and observe patient outcomes, and how they correlate with the treatment they received. Trial analysis of all admissions in 2018 identified 901 patients with an abdominal emergency, 59% (530) of which had surgical intervention, either a laparotomy or a laparoscopy. Scaling these numbers to the study period of 6.5 years, we expect to identify a total of over 5,800 patients with an intestinal emergency and over 3,400 patients undergoing surgery. All UK hospitals have to submit data on all their intra-abdominal procedures to the National Emergency Laparotomy Audit (NELA). From previous analysis of PHUT NELA data (11), at least 30% of patients having an operation will have been completed laparoscopically. This is a remarkably large proportion of laparoscopic procedures compared to the UK average (8% according to NELA database) and will provide us over 1,000 laparoscopies in our study data set.

The PHUT data set includes a sufficient number of outcomes for model development (rule of thumb: 10 outcomes per predictor variable (25)). This study will be looking at a patient population with high mortality. Initial analysis of 2018 data identified in-hospital mortality as the rarest outcome with 23 deaths (4.3%) of patients having surgery and 28 deaths (7.6%) of patients not having surgery. Other outcomes occur in greater numbers. Collective numbers for the 6.5 year study period will therefore provide us with enough outcomes for the development of logistic regression models. The data set will be tested for separation and Firth's correction applied if necessary (26). Based on these numbers, we will be able to establish statistically significant correlations from this data set from a single hospital.

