### 10.2 Data analysis

Extracted data will be cleaned and quality controlled prior to analysis to ensure all relevant patients have been extracted. Given that our analysis will use only routinely collected, clinical data, missing values are unlikely to pose an issue. Initial analysis of 2018 data confirmed that clinical data within 24h of admission was almost fully complete for a remarkable >97% of admissions, meaning there is likely no need to impute data. We will test whether excluding admissions with missing data will introduce bias.

Our analysis can be broken down into the following steps:

- Comparison of the four treatment groups based on demographics, outcomes and medical pathway. This will include calculating mortality and long-term complication rates (Objective 2).
- Construct and compare risk models for each treatment group to predict short-term and long-term risk and to investigate the effect of both patient and hospital-level factors on outcome (Objective 3).

- Identify patients in each group who are abnormal for the group and might have fared better with a different treatment, using clustering algorithms (Objective 4).

After splitting the data set into subsets for each of the four patient groups using diagnosis and procedure codes (see above), mortality and long-term complication rates will be calculated for each group. Longer-term follow-up will include rates of re-admission to hospital, additional theatre visits and development of new medical conditions, within one year of initial admission with an abdominal emergency. Results will provide updated estimates of the average risks of different surgical procedures as well as the risk of not having surgery. Results will be compared with P-POSSUM mortality. Patient groups will further be characterised the using patient factors. Parameters of interest will include but are not limited to age, sex, mortality, long-term complication rates, admission early warning scores (NEWS, LDTEWS and LDTEWS:NEWS), frailty, medical history (previous ICD-10 codes).

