Patient group characteristics will be summarised with proportions for nominal and ordinal variables, means and standard deviations for continuous variables having symmetric unimodal distributions, and medians and interquartile ranges for other continuous variables. Clinical outcomes will be reported as proportions with 95% confidence intervals. Statistical tests of differences in proportions (Chi - nominal variables) and means/medians (ANOVA/Kruskal-Wallis) will be performed. Post-hoc pairwise comparisons will be carried out using Scheffe's method for ANOVA and Dunn's test for Kruskal-Wallis results and Bonferroni corrections for Chi results with significance at  $p < 0.05$ .

In the next step, we will identify which patient characteristics affect the outcome for a specific care pathway. Candidate predictor variables of 30-day mortality will be assessed with simple univariable linear regression and check for non-linearity. For each treatment group, we will construct a logistic regression model with the candidate predictor variables and non-linear terms as needed. Logistic regression performance will be tested using "goodness of fit" and discrimination. Goodness of fit, the ability to correctly predict risk, will be evaluated using the Hosmer-Lemeshow statistic (28) and by 10-fold cross-validation. Discrimination, the ability to rank cases in terms of risk, will be assessed using the Area Under the Receiver Operating Characteristic Curve (AUROC) (29). The relative importance of individual parameters will be assessed by the parameters Wald and t-statistics.

The last objective is to determine outlier clusters of patients who might have fared better on a different care pathway. For each treatment group, machine learning classification algorithms will be used to identify homogenous clusters of admissions in terms of their attributes. Each clustering will be reported by its method, number of clusters and intracluster correlation coefficients (ICCs) with 95% confidence intervals and used to extend the logistic regression risk model for the treatment group to see if the model is improved as measured by a likelihood ratio test. Where this is the case the patient subgroups corresponding to the clusters will be analysed in terms of their clinical characteristics.

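### Hosmer-Lemeshow is the only calibration statistic named, the cross-validation has no calibration measure attached, and the test's p-value depends on group size without giving the size of error

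*Protocol*

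**What the plan says.** Among the analysis steps in protocol section 10.2 is "Construct and compare risk models for each treatment group to predict short-term and long-term risk". For the modelling itself: "For each treatment group, we will construct a logistic regression model with the candidate predictor variables and non-linear terms as needed". Performance is then split into two properties. For correct risk prediction: "Goodness of fit, the ability to correctly predict risk, will be evaluated using the Hosmer-Lemeshow statistic (28) and by 10-fold cross-validation". For ranking, the AUROC is used.

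No calibration slope, calibration-in-the-large, calibration plot or Brier score is named. The section does not say which quantity the cross-validation yields, whether Hosmer-Lemeshow is computed on the fitting data or on held-out predictions, or by what criterion the treatment-group models are compared.

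Section 6.2 (objective 3) uses the predicted risks of death to identify care pathways. Section 12.3 plans patient documents that convey individual risk.

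**The concern.** The protocol treats a Hosmer-Lemeshow result as showing that risks are predicted correctly. The test measures evidence against perfect fit. It does not estimate how far predicted risks are off.

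Two consequences follow. First, a logistic model reproduces the overall death count of the data it was fitted to, and its coefficients are tuned to those data, so the test has little power there against overfitting. Second, the p-value for a given error falls as patients and deaths accumulate, so results from groups of different size are not on one scale.

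The risks of each treatment option come from a separate model. If one model is more overfitted than another, its high risks are too high and its low risks too low by a different amount. That can alter which option looks safer for a given patient, and a Hosmer-Lemeshow p-value would not show it reliably.

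**Working it through.** **Group sizes from section 8.** The inputs are "Trial analysis of all admissions in 2018 identified 901 patients with an abdominal emergency, 59% (530) of which had surgical intervention", "at least 30% of patients having an operation will have been completed laparoscopically" and "in-hospital mortality as the rarest outcome with 23 deaths (4.3%) of patients having surgery and 28 deaths (7.6%) of patients not having surgery".
- Total: 901 × 6.5 = 5,856, matching the stated figure of over 5,800.
- Surgery: 530 × 6.5 = 3,445, matching over 3,400.
- Laparoscopy: 0.30 × 3,445 = 1,033, matching over 1,000.
- Laparotomy: 0.70 × 3,445 = 2,411.
- No surgery: (901 − 530) × 6.5 = 371 × 6.5 = 2,411. The match with laparotomy is a coincidence. This group splits into two pathways of unstated size.
- In-hospital mortality: 23/530 = 4.3%; 28/371 = 7.5% (stated as 7.6%, immaterial).
- Deaths in the laparoscopy group, if the all-surgery rate applies: 1,033 × 0.0434 ≈ 45.

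**Simulation set-up.** These are assumptions, since the protocol fixes no predictor count: five true predictors, the rest noise, standard deviation of the true linear predictor 1.2, no variable selection. Hosmer-Lemeshow = Σ (O − E)² / [E(1 − E/n_g)] over ten risk groups, with 8 df on fitting data and 10 df on held-out predictions. The slope in new patients is estimated in 20,000 fresh patients (ideal value 1). There were 300 runs per row, so the Monte Carlo standard error is about 1.3 points at 5% and 2.2 points at 83%.

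**Step 1: does the test see overfitting?** All rows use 4.3% deaths.

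| n | Predictors | Deaths per predictor | Rejected, fitting data | Slope in new patients | Rejected, pooled held-out | Cross-validated slope |
|---|---|---|---|---|---|---|
| 1,033 | 5 | 8.8 | 7% | 0.91 | 11% | 0.86 |
| 1,033 | 10 | 4.5 | 5% | 0.84 | 22% | 0.77 |
| 1,033 | 20 | 2.2 | 8% | 0.68 | 83% | 0.62 |
| 2,411 | 10 | 10.5 | 3% | 0.92 | 7% | 0.89 |
| 2,411 | 20 | 5.3 | 4% | 0.84 | 27% | 0.81 |

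Independent repeats at n=1,033 with 10 to 20 predictors put rejection on the fitting data between about 3 and 9%, with slopes of about 0.83 to 0.67. That is close to the nominal 5% despite clear overfitting. The cross-validated slope shows the problem each time, running 0.03 to 0.07 below the slope in new patients.

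**Step 2: same error, different group size.** Predictions were set as logit = b0 + 1.25 × (true logit − b0), which gives a slope of 1/1.25 = 0.80 (1,000 runs, standard error about 1.4 points at 28% and 71%).
- 4.3% mortality: rejected 28% at n=1,033, 71% at n=2,411.
- 7.6% mortality: rejected 43% at n=1,033, 87% at n=2,411.

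This set-up also raises the mean prediction, from 4.3% to 5.6% in the first case, and cross-validated predictions would largely not do that. Resetting the intercept so that the mean prediction equals the true mean, with the slope still 0.80 (4,000 runs), gives:
- 4.3% mortality: 31% at n=1,033, 48% at n=2,411.
- 7.6% mortality: 36% at n=1,033, 60% at n=2,411.

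The dependence on size and deaths remains but is weaker.

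**The case against.** **Cross-validation is already in the sentence.** A reader might infer that Hosmer-Lemeshow is the protocol's only check of risk prediction. It is not: 10-fold cross-validation is named beside it, and step 1 shows that held-out predictions can expose overfitting. What stands against the plan is narrower. Cross-validation is a procedure with no calibration measure attached, and Hosmer-Lemeshow on its output still yields a p-value and not an amount of error.

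**Two tempting readings are not protocol text.** Nothing says that the test is confined to the fitting data, so the low rejection rates in step 1 are conditional on that use. Nothing says that the models will be compared by Hosmer-Lemeshow p-value, or that a non-significant result will be reported as accurate prediction. Section 10.2 plans a comparison without naming its criterion.

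**Overfitting may be mild.** Section 8 cites 10 outcomes per predictor. If that were kept within every group, the laparoscopy model would have about 45/10 ≈ 4 predictors, and the table's rows nearest the rule have slopes of 0.91 and 0.92. But the rule is argued there from collective numbers, and the characteristics listed in section 10.2 are open-ended, with non-linear terms added. The candidate-predictor step also concerns 30-day death, and section 8 calls in-hospital death the rarest outcome, so 30-day models would have more events and less overfitting.

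**Convention and the SAP.** The combination of Hosmer-Lemeshow, AUROC and cross-validation is conventional and referenced, and details of calibration reporting often sit in an SAP, which is not shown. Their absence alone would be no finding. The point rests on what the protocol does state: it chose this statistic and described it as measuring correct prediction.

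**Conclusion.** The point holds as an inexpensive improvement to a stated choice; the protocol does not contradict itself here. Hosmer-Lemeshow is a poor basis for judging or comparing the four treatment-group models.

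On fitting data it would pass most overfitted models: about 3 to 9% rejected where the slope is about 0.83 to 0.67. On held-out predictions it detects more (about 22 to 83%), but for an equal slope of 0.80 at 4.3% mortality its rejection rate moves from 28% to 71%, or from 31% to 48% with the mean held correct, merely because the group grows from 1,033 to 2,411.

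The first result depends on 10 to 20 predictors, the assumed predictor strength, and applying the all-surgery death rate to laparoscopy. The second does not depend on predictor count. Group sizes follow section 8. The synopsis plans 2,500 patients; on that figure the laparoscopy group would be about 2,500 × 530/901 × 0.30 ≈ 441, with about 19 in-hospital deaths, and overfitting for a given number of predictors would be worse.

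**What to change.** Replace the goodness-of-fit sentence in section 10.2 with wording such as:

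*Correct risk prediction will be assessed for each treatment-group model by the calibration slope and calibration-in-the-large, each with a 95% confidence interval, and by a smoothed calibration plot, all from the pooled out-of-fold predictions of the 10-fold cross-validation, with any data-driven choice of predictors or non-linear terms repeated in each fold. Groups will be compared on these estimates. The Hosmer-Lemeshow statistic is supplementary. Where the slope is well below 1, the coefficients will be shrunk by it and the intercept re-estimated before risks are quoted.*

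The study team should set in advance what counts as well below 1. Pooling matters: one laparoscopy fold has about 103 patients and 4 to 5 deaths, or under 0.5 expected deaths per risk group, which is too few for a test within folds. Calibration-in-the-large will usually look good in internal cross-validation, so the slope and the plot carry most of the information.

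The cost is a little more analysis, since the cross-validation is already planned. Reported fit will look less favourable, and slope intervals will be wide in groups with few deaths.

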### **6.2 Objectives**

1. Identify all patients with a condition that would qualify them for emergency abdominal surgery, both laparotomy and keyhole (laparoscopic) procedures, regardless of whether they had surgery

or not. This will be done by filtering electronic hospital records for appropriate diagnosis and operation codes.

2. Provide updated estimates of the average risk of death for different treatment options, including surgical and non-surgical intervention, using statistical analysis of short-term and long-term outcomes. Describe health characteristics of the typical patient population receiving one of the treatment options, based on their clinical data and an established risk index.
3. Logistic regression will be used to predict the risk of death for each patient group and each treatment option, which will allow identification of the best care pathways given a patient's health characteristics.
4. Identify patients who would have likely benefited from a different care pathway than the one they received, using machine learning classification algorithms

Our analysis will form the foundation for the establishment of four well-defined care pathway options, each with the patient's best interest in mind: laparotomy, laparoscopy, other alternative treatment, and end of life care.

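### The section 10.2 method for Objective 4 keeps or drops clusters by a within-group likelihood ratio test, so it does not carry out the cross-pathway comparison that the objective and the Synopsis call for

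*Protocol*

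**What the plan says.** **The aim.** Protocol section 6.2 gives Objective 4 as: "Identify patients who would have likely benefited from a different care pathway than the one they received, using machine learning classification algorithms". The outline in section 10.2 has: "Identify patients in each group who are abnormal for the group and might have fared better with a different treatment, using clustering algorithms". The last paragraph of section 10.2 opens: "The last objective is to determine outlier clusters of patients who might have fared better on a different care pathway".

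**The method.** The same paragraph then sets out three steps.

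1. Clustering: "For each treatment group, machine learning classification algorithms will be used to identify homogenous clusters of admissions in terms of their attributes".
2. Testing, with the clusters as the added terms: "extend the logistic regression risk model for the treatment group to see if the model is improved as measured by a likelihood ratio test".
3. Use of the result: "Where this is the case the patient subgroups corresponding to the clusters will be analysed in terms of their clinical characteristics".

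**Cross-option elements elsewhere.** Objective 3 in section 6.2 states: "Logistic regression will be used to predict the risk of death for each patient group and each treatment option". The outline in section 10.2 has: "Construct and compare risk models for each treatment group to predict short-term and long-term risk". The Synopsis (Secondary Objectives) goes further and says that predicting risk by patient group and treatment option will allow the best pathway to be found for each cluster. Sections 7.1 and 7.3 likewise pair risk prediction for the different treatments with clusters of similar patients, in order to find lower-risk options for different patient groups.

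**The concern.** To say that a patient would have fared better elsewhere is to compare two risks: the risk under the pathway received and the risk under another. The method paragraph has no step that estimates the second. Its only decision rule is whether a clustering improves the model of the group in which it was found. Passing that test shows that the group's model had missed some variation in risk. It does not show the direction, since patients in a flagged cluster may have done better or worse than predicted, and it says nothing about the alternative.

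Followed as written, Objective 4 would deliver clusters that mark lack of fit, reported under an aim about patients who might have fared better on a different pathway. Readers could take them for patients on the wrong pathway. Section 15.1 says the findings will inform new care pathways and patient information, so that misreading would matter.

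**Working it through.** **What the test can see.** For treatment group g, let model 0 hold the candidate predictors and model 1 add the cluster terms. The statistic is

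LR = 2 × (ℓ1 − ℓ0),

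where both log-likelihoods are sums over the patients of group g only, because section 10.2 splits the data by group before modelling. No outcome from any other group enters. Whatever the risk under another pathway, LR takes the same value.

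**Illustration by simulation.** The inputs are assumptions, not document figures: one group of 2,400 patients, intercept risk 4%, one covariate with log-odds 0.7 per SD, a known cluster holding 15% of patients, a test on 1 degree of freedom at 0.05, and 500 runs. The alternative pathway is laid over the same data, so its irrelevance to the test holds by construction. The runs only put numbers on it.

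| Cluster odds ratio in own group | Test significant | Cluster mortality, own pathway | If the alternative halves the odds | If the alternative doubles the odds |
|---|---|---|---|---|
| 2.5 | 98% of runs | 11.1% | 6.0% | 19.4% |
| 1.0 | 6% of runs | 4.9% | 2.6% | 9.2% |

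In the first row a flagged cluster fits a better or a much worse outcome elsewhere equally well. In the second row the test rejects at about its nominal level, so the cluster is usually dropped even where the alternative would have nearly halved mortality.

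**How precise a direct contrast could be.** The protocol gives no figure for Objective 4, so there is none to reproduce. Inputs from section 8, for 2018: 901 patients, 530 operated, hence 901 − 530 = 371 not operated; in-hospital deaths 23 and 28.

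- p1 = 23/530 = 4.34%; p0 = 28/371 = 7.55%; crude difference 3.2 points (3.3 from the printed 7.6% and 4.3%).
- Cohort by the section 8 scaling: 901 × 6.5 = 5,856 (section 8 says over 5,800), with 371 × 6.5 = 2,411 not operated and 530 × 6.5 = 3,445 operated.
- Cohort by the Synopsis planned sample size: 2,500, which at the same split is 1,029 and 1,471.
- Half-width = 1.96 × √[p0(1 − p0)/n0 + p1(1 − p1)/n1].

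For a subgroup holding 25% of each group:

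- 5,856: n0 = 603, n1 = 861; 1.96 × √(0.0698/603 + 0.0415/861) = 2.5 points.
- 2,500: n0 = 257, n1 = 368; 1.96 × √(0.0698/257 + 0.0415/368) = 3.8 points.

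These describe the precision available to a repair. They do not measure the defect, which is independent of sample size.

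**The case against.** **The protocol does intend a cross-option comparison.** A reader of the last paragraph of section 10.2 alone might infer that the study never plans to compare clusters across pathways. The documents do not support that. The Synopsis ties predicted risk under each option to the best pathway for each cluster, sections 7.1 and 7.3 pair the two ideas, and Objective 3 supplies a model per treatment. This stands, and it narrows the point: the intention is stated, but the method paragraph does not carry it out.

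**This may be detail for a statistical analysis plan.** How models are applied to clusters often is. Here, however, the protocol writes down a specific gate and a specific use of its result. A later plan that followed the text would inherit a gate that can discard the very clusters Objective 4 is looking for. That is a stated rule that misses its aim, not an omission.

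**The language is cautious.** Section 10.2 says only that patients might have fared better, section 4.3 itself raises unmeasured confounding for the earlier cohort study, and section 15.3 presents this study as a first step. All fair, and the method paragraph does not itself claim that a significant test proves benefit elsewhere. But section 6.2 uses the stronger claim of likely benefit, and no caveat is attached to Objective 4.

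**The precision figures could be over-read.** The half-width equals the crude 3.2 points at 369 against 527 patients, and 369/1,029 = 36%. A reader might infer that with 2,500 patients only subgroups above about a third of each group could be informative. The documents do not support that rule. It takes the crude average difference as the benchmark although Objective 4 looks for atypical patients, it assumes the same fraction of both groups at average risk, and it uses in-hospital death, which section 8 calls the rarest outcome, where section 10.2 models 30-day mortality.

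**Conclusion.** The point holds for Objective 4 only. Its three method steps use data from one treatment group at a time, and the likelihood ratio gate carries no information on outcome under another pathway at any sample size. The cross-option comparison promised in the Synopsis is therefore not delivered by the method as written, and the gate can work against it. This should be corrected before the cluster analysis is run. The per-treatment models of Objective 3 are not in question.

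The conclusion about the gate rests on the text and on the form of the likelihood, not on the simulation settings. The half-widths of 2.5 and 3.8 points are illustrative. They assume 2018 in-hospital mortality, equal subgroup fractions at average risk, and no adjustment or overlap restriction. They compare operated with not operated because section 8 gives deaths only for those two groups; contrasts among the four pathways would generally be less precise.

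**What to change.** In the last paragraph of section 10.2:

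- State that the likelihood ratio test is a check of model fit and does not decide which clusters are examined for Objective 4.
- For each cluster, compare predicted mortality under the option received with that under the alternatives, using the per-treatment models already planned for Objective 3.
- Limit each comparison to patients whose characteristics occur in both groups compared, and make none where there is no overlap. This may arise for the group that the Synopsis defines by futility of treatment.
- Report the contrasts with confidence intervals and label them hypothesis-generating, citing the unmeasured confounding raised in section 4.3.

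A pooled model with treatment-by-covariate terms is an optional alternative source of the predictions.

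If the contrast is not wanted, reword Objective 4 in the Synopsis, section 6.2 and both places in section 10.2 as a descriptive search for patients atypical of their treatment group.

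Cost: rewording changes only protocol text. The contrast reuses planned models and data already to be extracted. Its price is fewer assessable patients once overlap is required, and wide intervals, more so if the cohort is nearer the Synopsis figure of 2,500 than the 5,856 implied by section 8.

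### Section 10.2 reports clusters by ICCs with 95% intervals on an unnamed variable; on the clustering attributes these would almost always lie above zero even with no clusters

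*Protocol*

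**What the plan says.** Objective 4 looks for patients who may have done better on a different care pathway. For each treatment group, Protocol section 10.2 states that "machine learning classification algorithms will be used to identify homogenous clusters of admissions in terms of their attributes". The next sentence fixes what is reported for a clustering: the method, how many clusters there are, and "intracluster correlation coefficients (ICCs) with 95% confidence intervals". The variable behind the ICC, the interval method and any reference value are not given.

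The same sentence goes on to say that the clusterings will be "used to extend the logistic regression risk model for the treatment group to see if the model is improved as measured by a likelihood ratio" (that is, by the test of that name). The step that follows depends on its result: "Where this is the case the patient subgroups corresponding to the clusters will be analysed in terms of their clinical characteristics". The 10-fold cross-validation in section 10.2 belongs to the logistic models, not to the clusters.

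**The concern.** A clustering algorithm is asked to make groups that are alike in a set of attributes. If the ICC is then computed on those attributes in those patients, it measures what the algorithm has just maximised. Some within-cluster correlation must appear whether or not the population contains subgroups. The usual ICC interval assumes that cluster membership was known before the data were seen, so it makes no allowance for the search.

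A reader shown an ICC of 0.4 with a narrow interval well above zero will take it as evidence that the groups are real. These clusters describe patients for whom another pathway is suggested, and the protocol intends its results to inform care pathways and patient information (sections 6.2 and 15.1). A measure that looks convincing when nothing is there is a poor description of their quality.

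**Working it through.** **Inputs from the protocol (section 8).** The protocol states no ICC value or threshold, so its figures serve only to set realistic group sizes. The 2018 trial analysis "identified 901 patients with an abdominal emergency, 59% (530) of which had surgical intervention", and the protocol proceeds by "Scaling these numbers to the study period of 6.5 years":

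- Emergencies: 901 × 6.5 = 5,856.5 (stated: over 5,800).
- Surgical patients: 530 × 6.5 = 3,445 (stated: over 3,400).
- Laparoscopies, taking "at least 30% of patients having an operation will have been completed laparoscopically": 0.30 × 3,445 = 1,033.5 (stated: over 1,000).
- Laparotomies: 0.70 × 3,445 = 2,411.5. Non-surgical patients: (901 − 530) × 6.5 = 371 × 6.5 = 2,411.5.

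The stated figures reproduce. Group sizes of 1,000 and 2,400 were used.

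**Assumptions, because the protocol fixes none of these.** k-means (best of 3 starts), k = 3, 4 or 6 clusters, p = 2, 5, 10 or 20 attributes, normally distributed, 100 replicates per setting. Every data set came from one multivariate normal population, so there were no clusters to find.

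**Formulas.** One-way ANOVA with F = MSB/MSW and n0 = (N − Σnᵢ²/N)/(k − 1):

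- ICC = (F − 1)/(F − 1 + n0).
- Lower 95% limit: the same expression with F replaced by F divided by the 0.975 quantile of the F distribution on k − 1 and N − k degrees of freedom.

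**Result 1: ICC on the clustering attributes, independent attributes, n = 1,000.**

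| Attributes | Mean ICC, k = 3 / 4 / 6 | Lower limit above 0, k = 3 / 4 / 6 |
|---|---|---|
| 2 | 0.64 / 0.71 / 0.78 | 100% / 100% / 100% |
| 5 | 0.30 / 0.36 / 0.45 | 97.6% / 100% / 100% |
| 10 | 0.17 / 0.20 / 0.25 | 96.2% / 98.7% / 99.7% |
| 20 | 0.09 / 0.11 / 0.14 | 91.5% / 95.6% / 99.2% |

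With no clusters, 2.5% of lower limits should exceed zero. At n = 2,400 the mean ICCs differ by at most 0.01, and 96.1% to 100% of lower limits exceed zero.

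**Result 2: is the labelling the cause?** With random labels on the same attributes, the lower limit exceeded zero in 1% to 4.5% of cases. With the k-means labels and an independent variable not used for clustering, the mean ICC was about 0 and the lower limit exceeded zero in 0% to 6% of runs. The interval behaves when the labels do not come from the variable being assessed, and fails when they do.

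**Result 3: correlated attributes.** Age, frailty, co-morbidities, vital signs and blood tests (section 10.1) are unlikely to be independent. Again with no clusters, n = 1,000, k = 4 and 40 replicates, the mean ICCs were:

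| Attributes | Correlation 0 | 0.3 | 0.5 |
|---|---|---|---|
| 10 | 0.20 | 0.40 | 0.56 |
| 20 | 0.11 | 0.37 | 0.55 |

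At correlations 0.3 and 0.5 every lower limit exceeded zero. Across 5 to 20 attributes at this size and k, the null mean ranged from 0.11 to 0.61. The correlations are assumed values.

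**The case against.** **The ICC selects nothing.** This is the strongest objection, and it stands. No ICC threshold is set; the likelihood ratio test decides what is analysed further. That test uses mortality, which did not form the clusters if the attributes are admission characteristics. With no clusters, 6 attributes at correlation 0.2, k = 4 and a correctly specified risk model, noise clusters passed it in 7% (n = 1,000) and 5% (n = 2,400) of runs, close to nominal. A reader might infer that spurious subgroups will be chosen and published on the strength of their ICCs; section 10.2 does not support that. The test does not make the ICC meaningful, however, because it asks whether labels add to mortality prediction and not whether subgroups exist. With no clusters (n = 2,400, 5 attributes, k = 4) it passed in 27% of runs when the risk model omitted a quadratic term and in 13% when it omitted an interaction. The planned non-linear terms would reduce the first figure. That is a separate matter.

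**The variable and the interval method are inferred.** This also stands. If the ICC were of an external variable not used for clustering, the problem would vanish, as Result 2 shows. A bootstrap that repeats the clustering is not excluded. But the ICC sentence follows directly on homogeneity of attributes, and no other variable is offered.

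**High by construction would be too strong.** A reader might infer that the null ICC is always large. With 20 independent attributes it is 0.09 to 0.14. Inflated above zero is accurate; the amount depends on the attributes.

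**This is detail for an analysis plan.** Partly so: the algorithm, attributes and stability checks may be specified there, and their absence here is no error. The protocol itself, however, fixes the ICC with its interval as the reported measure.

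**Conclusion.** The point holds as a conditional one. If the ICCs are computed on the attributes that formed the clusters, in the same patients and with standard intervals, they and their intervals will suggest structure that need not exist. The null mean is about 0.1 to 0.6 for 5 to 20 attributes, and higher with only two (0.64 to 0.78). With independent attributes, 92% to 100% of lower limits lie above zero where 2.5% should.

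This rests on the natural reading of the ICC variable, membership treated as fixed, k-means, normal attributes and the assumed values of k, p and correlation. Categorical attributes, and groups smaller than 1,000, were not simulated.

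The consequence is a misleading statement of cluster quality under Objective 4. It does not decide which clusterings are carried forward. The matter is minor and cheap to correct.

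**What to change.** In section 10.2, or in the analysis plan with a pointer from it:

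1. Name the variable or variables on which the ICC is computed, and the interval method.
2. State that an in-sample ICC on the clustering attributes, with its interval, is descriptive and will not be presented as evidence that clusters exist.
3. Run the same clustering procedure on simulated no-cluster data with the same size and correlation structure as the observed attributes. Report the observed ICC against that distribution, and describe clusters that do not exceed it as unsupported.
4. Report bootstrap stability (for example adjusted Rand) alongside, as a supplement and not as proof.

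Two simpler remedies are not enough alone. In correlated data with no clusters, bootstrap adjusted Rand was 0.90 to 0.95 for two clusters, so stability can endorse an arbitrary split. Held-out ICCs on the same attributes stayed as high as the in-sample values. Hence the no-cluster reference.

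The cost is a little computing and a few sentences, with no new data. The downside is that some clusters will be reported as unsupported or unstable.
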